13.1 Accounting for between-subjects variation in starting opioid dose

The study has been designed to account for between-subjects variation in the starting dose and quantal dose of opioid medication, while also allowing calculation of standardized efficacy endpoints. The opioid dose reduction process is complicated by that fact that there are quantal doses of opioid medication. For example, for methadone, which is commonly prescribed for RLS, the minimum pill size is 5mg and the quantal size is 2.5mg because pills can be broken in half.

All subjects initially participate in Phase 1, which involves the smallest reduction in opioid dose of greater than or equal to 20% of the starting dose. Subjects who tolerate Phase 1 without a clinically significant increase in RLS symptoms will advance to Phase 2, which involves the smallest additional reduction in opioid dose that also represents a total reduction of greater than or equal to 1/3 of the starting dose. Subjects who tolerate Phase 2 without a clinically significant increase in RLS symptoms will have the option to complete Phase 3, which involves an additional reduction in opioid dose. Once the subject completes a Phase where no further reduction is possible (e.g. a subject reaches 0mg in Phase 1 or 2), they will complete the study at the end of that Phase.

For example, in the case of methadone, the minimal quantal dose reduction is 2.5mg. Therefore, for methadone (**Table 4**):

- a subject on a 10mg starting dose would reduce to 7.5mg (25% reduction) in Phase 1 and 5.0mg (50% total reduction) in Phase 2. The endpoints related to $\geq 20\%$ reduction would be evaluated in Phase 1 and the endpoints related to $\geq 1/3$ reduction would be evaluated in Phase 2.
- a subject on a 7.5mg starting dose would reduce to 5.0mg (1/3 reduction) in Phase 1 and 2.5mg (2/3 total reduction) in Phase 2. The endpoints related to both $\geq 20\%$ reduction and $\geq 1/3$ reduction would be evaluated in Phase 1.
- a subject on a 5.0mg starting dose would reduce to 2.5mg (50% reduction) in Phase 1 and 0mg (100% total reduction) in Phase 2. The endpoints related to both $\geq 20\%$ reduction and $\geq 1/3$ reduction would be evaluated in Phase 1.
- a subject on a 2.5mg starting dose would reduce to 0mg (100% reduction) in Phase 1 and complete the study at the end of Phase 1. The endpoints related to both $\geq 20\%$ reduction and $\geq 1/3$ reduction would be evaluated in Phase 1.

CONFIDENTIAL

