13.2 Run-in and Assessment periods

[figure not shown]
Each Phase involves a 1-2 week run-in period followed by a 1-week assessment period. Assessment periods are primarily designed for endpoint evaluation. Run-in periods are designed for two reasons: (i) to provide a run-in phase to optimize instructions for NPNS device self-administration (e.g. timing and intensity) and (ii) so that any opioid withdrawal symptoms unrelated to the RLS condition resolve prior to the assessment period. Each run-in period will last a minimum of 1-week and a maximum of 2-weeks.

The investigator is permitted to adjust the instructed schedule of opioid medication and/or NPNS usage during a Step-Down based on clinical evaluation of response to opioid treatment and NPNS.

CONFIDENTIAL

All information contained in this document is confidential and is the sole property of Noctrix Health, Inc.
Any reproduction in part or whole without the written permission of Noctrix Health, Inc. is prohibited.

Figure 1. Flowchart of Run-in and Assessment periods for Phases 1 & 2

Additionally:

[figure not shown]
- If clinically significant opioid withdrawal symptoms unrelated to RLS become intolerable during the run-in period for a given Phase, participation will be discontinued and data from the subject will not count towards the efficacy endpoints for that Phase.
- If opioid withdrawal symptoms related to RLS become intolerable at any point during a run-in period, participation will be discontinued and the subject will count towards the efficacy endpoints for that Phase.
- The investigator may decide that participation should be discontinued at any time if there are excessive opioid withdrawal symptoms, even if those symptoms are tolerable.
- If opioid withdrawal symptoms become intolerable mid-week during a run-in period, participation will be discontinued.
- In all cases, efficacy outcome measures CGI-I and IRLS will be assessed at study exit but will not be included in analysis of the efficacy endpoints unless opioid withdrawal symptoms related to RLS was the primary reason for discontinuation.
- The Extension Phase is optional and requires approval by both the investigator and the participant. The structure of this phase is similar phases 1 and 2.

CONFIDENTIAL

All information contained in this document is confidential and is the sole property of Noctrix Health, Inc.
 Any reproduction in part or whole without the written permission of Noctrix Health, Inc. is prohibited.

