17.1. Efficacy

In the absence of an adjunctive treatment, a reduction in opioid dose will cause an increase in RLS symptoms. The efficacy of NPNS will be assessed by its capacity to prevent this increase in RLS symptoms. Subjects who discontinue due to nonspecific opioid withdrawal symptoms will not be included in the efficacy analysis but will be considered in the safety analysis. Efficacy endpoints will be calculated during the Assessment period except in cases of dropout during the run-in period(s); Section 13.2 describes how efficacy endpoints will be calculated in cases of dropout during the run-in period(s).

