17.1.1. Efficacy Endpoints

Endpoint 1 (Primary Endpoint): Percentage of subjects without a clinically significant increase in RLS symptoms (i.e. CGI-I score of 5 or less relative to baseline) during the first Phase involving an opioid dose reduction of $\geq 20\%$ relative to baseline.

Endpoint 2: Percentage of subjects without a clinically significant increase in RLS symptoms (i.e. CGI-I score of 5 or less relative to baseline) during the first Phase involving an opioid dose reduction of $\geq 1/3$ relative to baseline.

Endpoint 3: IRLS during the first Phase with an opioid dose reduction of $\geq 20\%$ relative to baseline.

Endpoint 4: IRLS during the first Phase with an opioid dose reduction of $\geq 1/3$ relative to baseline.

CONFIDENTIAL

 NOCTRIX HEALTH	Clinical Trial Investigational Plan, Protocol CT-03 (Opioid Reduction Study)	Document #: CT-2 (Previously CT-03) Rev: 4.0 (Superseded Rev C) CC#: 720 (Previously DCO #138) Effective: 09/24/2021
---	---	---

Endpoint 5: Maximal percentage reduction in opioid dose relative to baseline associated with a CGI-I score of 5 or less, averaged across subjects.

Of the 5 efficacy endpoints, only Endpoint 5 considers data during the Extension phase.

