17.1.2. Definition of Opioid Dose

Baseline opioid dose will be defined as the total weekly opioid dose that the subject reports taking during the week prior to study entry (7 days ending in EVAL 1). This value will be used to calculate the opioid doses for each Phase. If a subject reports taking a different opioid dose than instructed during an Assessment Period, the actual subject-reported opioid dose will be used to calculate the efficacy endpoints. In cases where a subject is taking multiple opioids concurrently, the morphine milligram equivalent (MME) will be used to standardize the baseline opioid dose, to calculate the opioid dose for each Phase, and to calculate opioid dose for the efficacy endpoints.

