17.1.3. Efficacy Analysis

Endpoints 1 and 2 are calculated with the following formula, respectively for Phases 1 and 2:

$100\% * ((X - Y) / (N - M))$, where

- N = Number of subjects who entered the Run-in period for the Phase.
- M = Number of subjects excluded during Run-in period due to non-RLS opioid withdrawal symptoms.
- Y = Number of subjects excluded during Run-in period primarily due to intolerable RLS symptoms.
- X = Number of subjects who complete Assessment period with no clinically significant worsening in Clinical Global Impression-Improvement scale (CGI-I) relative to Baseline, where a clinically significant worsening is defined by a score of 6 (Much worse) or 7 (Very much worse).

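### The 17.1.3 formula for Endpoints 1 and 2 has no opioid-dose condition and fixes the Phase, in conflict with 13.1, 17.1.1 and 17.1.2

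*Combined protocol and SAP*

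**What the plan says.** Section 17.1.1 defines Endpoint 1, the primary endpoint, as the percentage of subjects with CGI-I of 5 or less "during the first Phase involving an opioid dose reduction of" at least 20%. Endpoint 2 is the same with one third. Section 17.1.2 adds that if the dose reported in an Assessment Period differs from the instructed dose, "the actual subject-reported opioid dose will be used to calculate the efficacy endpoints".

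Section 17.1.3 gives the only formula, 100% × (X − Y)/(N − M). X is the "Number of subjects who complete Assessment period with no clinically significant worsening in Clinical Global Impression-Improvement scale". N is everyone who entered the run-in, M those excluded in the run-in for non-RLS withdrawal symptoms, and Y those excluded there mainly for intolerable RLS symptoms. On the Phase it states: "Endpoints 1 and 2 are calculated with the following formula, respectively for Phases 1 and 2".

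Section 13.1 sets the Phase 1 step as one "which involves the smallest reduction in opioid dose of greater than or equal to 20% of the starting dose". Its methadone examples include "a subject on a 7.5mg starting dose would reduce to 5.0mg (1/3 reduction) in Phase 1", with both endpoints then read in Phase 1. It says the same for 5 mg and 2.5 mg starters.

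Section 16.12 lists failure to keep to the reduced opioid dose as a ground on which a subject may, not must, be removed. Section 13.2 says that exit scores "will not be included in analysis of the efficacy endpoints unless opioid withdrawal symptoms related to RLS was the primary reason for discontinuation". Section 17.1.5 passes the study if Endpoint 1 exceeds 50%; the Synopsis plans 20 to 40 subjects.

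**The concern.** The objective is whether the device allows a meaningful opioid reduction, so a primary-endpoint success should mean that the reduction took place and RLS did not clearly worsen. The formula checks only the second half. A completer who drifted back towards the baseline dose and scored 5 or less enters X. Under 17.1.1, read on the dose that 17.1.2 requires, that subject has no Endpoint 1 value from Phase 1 and may acquire one in Phase 2. An analyst following 17.1.3 and one following 17.1.1 with 17.1.2 can report different primary results from the same data, and the pass rule is a bare point estimate in a small sample.

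A subject who departs from the instructed dose but remains at least 20% below baseline is not affected for Endpoint 1.

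**Working it through.** **Inputs.** The formula (17.1.3), the pass rule of more than 50% (17.1.5), N of 20 to 40 (Synopsis), the weekly baseline dose (17.1.2) and 2.5 mg methadone steps (13.1, Table 4). The plan has no power or sample-size figure to reproduce. Table 4 does reproduce: 10 to 7.5 mg is 2.5/10 = 25%, and 12.5 to 10 mg is 2.5/12.5 = 20.0%. M = Y = 0 below unless stated.

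**1. How small a departure crosses 20%.** For starting dose s, Phase 1 dose d and k extra 2.5 mg units in the Assessment week, the reduction is (7s − 7d − 2.5k)/(7s).
- s = 12.5, d = 10, k = 1: (87.5 − 72.5)/87.5 = 17.1%
- s = 10, d = 7.5, k = 2: (70 − 57.5)/70 = 17.9%
- s = 20, d = 15, k = 3: (140 − 112.5)/140 = 19.6%
- s = 7.5, d = 5, k = 3: (52.5 − 42.5)/52.5 = 19.0%
- Starters on 17.5 or 5 mg need five units, and those on 15 or 2.5 mg need six.

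**2. Retained, under-reduced completers with CGI-I of 5 or less** (numbers of subjects assumed).

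| Reading | 13 of 20 in X, 3 under-reduced | 24 of 40 in X, 4 under-reduced |
|---|---|---|
| 17.1.3 as written | 13/20 = 65.0% | 24/40 = 60.0% |
| No value | 10/17 = 58.8% | 20/36 = 55.6% |
| Non-success | 10/20 = 50.0% | 20/40 = 50.0% |

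If these subjects first reach 20% in Phase 2 and complete it, the rate lies between the first and last rows. For this group the literal formula gives the same rate or a higher one.

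**3. Number needed to reverse a pass.** A pass needs 11/20 or 21/40. Counted as non-successes, the smallest k with (x − k)/N ≤ 0.5 is 1 for 11/20 and 21/40, 3 for 13/20, 4 for 24/40 and 8 for 28/40. Dropped from both numerator and denominator, (x − k)/(N − k) ≤ 0.5 needs twice as many: 2, 2, 6, 8 and 16.

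**4. Groups where the difference runs the other way.**
- An under-reduced completer with CGI-I 6 or 7 is a failure under 17.1.3, but has no value from that Phase under 17.1.1 with 17.1.2, and the score ends participation. With one such subject, 10/20 = 50.0% (fail) becomes 10/19 = 52.6% (pass).
- A subject removed under 16.12 stays in N but is in neither X nor M, so is a failure under 17.1.3. The exit-score sentence in 13.2 can be read as excluding that subject. With three removals, 13/20 = 65.0% becomes 13/17 = 76.5%.

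**5. The fixed Phase.** The 7.5 mg starter reaches 2.5/7.5 = 1/3 in Phase 1, so 13.1 takes Endpoint 2 there; 17.1.3 takes it in Phase 2. A 2.5 mg starter finishes at the end of Phase 1 and so never enters N for Endpoint 2 under 17.1.3. By the same arithmetic a 15 mg starter (15 to 10 mg, 5/15 = 1/3) also reaches both thresholds in Phase 1.

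**6. The Y term.** Y subjects never complete the Assessment period, so they are not in X, yet they are subtracted. Each counts as −1 rather than 0. With X = 11, Y = 2, N = 20 (assumed), the formula gives 9/20 = 45.0%, against 11/20 = 55.0% if the two simply counted as failures.

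**The case against.** The strongest reply is that section 13 defines each Phase by its assigned reduction, so the first Phase at 20% or more is Phase 1 for everyone and 17.1.3 applies Endpoint 1 correctly. The reported-dose sentence would then serve Endpoint 5, the maximal reduction achieved. This answers the 17.1.1 conflict for Endpoint 1 only. Section 17.1.2 speaks of the efficacy endpoints in the plural, and on this reading it would do nothing for Endpoints 1 and 2. Section 13.1 still contradicts the fixed Phase for Endpoint 2. If 17.1.2 is instead taken to supply the dose condition, it does not say whether an under-reduced completer fails, drops out of the denominator or is read in Phase 2.

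It is also fair that the study is exploratory, open-label and single-arm with no hypothesis test, that 16.12 may remove some of these subjects, and that no rate of under-reduction is given. These points limit the weight of the issue but do not reconcile the sections.

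Two stronger readings are tempting. A reader might infer that the formula always favours a pass; step 4 shows that it does not. A reader might also infer that the plan is in error over retained subjects who raise a non-opioid RLS or sleep medication. The documents do not support that: 16.12 already lists such a change as a ground for removal, no stated rule is shown to be wrong, the frequency is unknown, and how to count those who stay is an estimand choice on which statisticians can reasonably differ.

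**Conclusion.** The inconsistency is real. Section 17.1.3 has no dose condition and fixes the Phase, against 17.1.2, against 17.1.1 read on the reported dose, and against 13.1. For retained, under-reduced completers with CGI-I of 5 or less, the literal formula gives the same or a higher rate than the alternatives. For under-reduced completers with CGI-I 6 or 7, and for removed subjects if 13.2 excludes them, it gives a lower one.

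The size depends on how near the result is to 50%: one reclassification can decide 11/20 or 21/40, while 28/40 would need eight non-successes. For a 12.5 mg methadone starter, one extra 2.5 mg unit in the week is enough to fall below 20%. The numbers of affected subjects are assumptions, and the rate examples in steps 2 to 4 take M = Y = 0. Handling of non-opioid medication changes is an optional clarification and not part of this conclusion.

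**What to change.** Change analysis rules only, leaving dosing and removal as they are, and do it before the data are reviewed. Reconcile 17.1.3 with 13.1, 13.2, 17.1.1 and 17.1.2.

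- Replace the fixed Phase assignment with evaluation in the first Phase whose reported Assessment-week dose is at least 20% (Endpoint 2: at least one third) below baseline, and require that reduction for X.
- State one classification for completers who never report the reduction, whatever their CGI-I score, and one for subjects removed under 16.12. Word both alike in 13.2 and 17.1.3.
- Say which Phase's M and Y apply to a subject whose Endpoint 1 value moves to Phase 2.
- Do not cite the current formula as precedent for counting these subjects as non-successes, because it subtracts Y.
- Report how many subjects are affected, with a sensitivity analysis under the alternative classification, applied equally to CGI-I of 5 or less and of 6 or 7.

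Optionally, report the number of retained subjects who raise a non-opioid RLS or sleep medication, with a sensitivity analysis from the scheduled medication assessments.

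The cost is a few sentences in 17.1.3, one aligned sentence in 13.2 and one table. The observed rate may change slightly, and a few subjects would be evaluated in Phase 2.

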17.1.4. Planned subgroup analysis

Subgroup analysis will be planned based on the location of RLS symptoms in the body, for the following subgroups:

CONFIDENTIAL

All information contained in this document is confidential and is the sole property of Noctrix Health, Inc.
Any reproduction in part or whole without the written permission of Noctrix Health, Inc. is prohibited.

 NOCTRIX HEALTH	Clinical Trial Investigational Plan, Protocol CT-03 (Opioid Reduction Study)	Document #: CT-2 (Previously CT-03) Rev: 4.0 (Superseded Rev C) CC#: 720 (Previously DCO #138) Effective: 09/24/2021
---	---	---

- subjects who experience RLS symptoms that are most significant below the knees (lower legs and/or feet)
- subjects who experience RLS symptoms that are most significant above the knees (upper legs) or equally significant above and below the knees

17.1.5. Criterion for Success

If Endpoint 1 is greater than 50 percent, then the study will pass the Primary Efficacy endpoint.

17.2. Safety

Safety will be assessed primarily based on response to NPNS. However, the proportion of subjects excluded due to non-RLS opioid withdrawal symptoms will also be considered in the safety analysis.

17.2.1. Safety Endpoints

Endpoint 1: Frequency of Grade 2 of higher NPNS-related adverse events, as indicated by a relatedness assessment of Probable or Definite.

Endpoint 2: Frequency of Grade 3 or higher NPNS-related adverse events.

Endpoint 3: Percentage of subjects who withdraw from study during Phase 1 or Phase 2 citing lack of tolerability of NPNS as the primary reason for withdrawal.

Endpoint 4: Percentage of subjects who are discontinued from study due to non-RLS opioid withdrawal symptoms during Phases 1 or 2.

Endpoint 5: Percentage of subjects who withdraw from study citing lack of tolerability of NPNS as the primary reason for withdrawal during Phase 1

Endpoint 6: Percentage of subjects who withdraw from study citing lack of tolerability of NPNS as the primary reason for withdrawal during Phase 2.

Endpoint 7: Percentage of subjects who are discontinued from study due to non-RLS opioid withdrawal symptoms during Phase 1.

Endpoint 8: Percentage of subjects who are discontinued from study due to non-RLS opioid withdrawal symptoms during Phase 2.

Additional exploratory endpoints:

CONFIDENTIAL

All information contained in this document is confidential and is the sole property of Noctrix Health, Inc.
Any reproduction in part or whole without the written permission of Noctrix Health, Inc. is prohibited.

 NOCTRIX HEALTH	Clinical Trial Investigational Plan, Protocol CT-03 (Opioid Reduction Study)	Document #: CT-2 (Previously CT-03) Rev: 4.0 (Superseded Rev C) CC#: 720 (Previously DCO #138) Effective: 09/24/2021
---	---	---

Endpoint 9: Reduction in severity of side-effects related to opioid use (not withdrawal) that were present at baseline during Phase 1 and Phase 2 assessment periods.

** Note that data from the Extension Phase is included in analysis of Endpoints 1 and 2 but not analysis of Endpoints 3-9.*

17.2.2. Safety Analysis

AEs occurring at any time during the study will be described and the investigator or designee will grade its severity, its relationship to device usage, and its relationship to opioid withdrawal.

The frequency of the following categories of AEs will be determined: device-related AEs, AEs related to opioid withdrawal, AEs unrelated to opioid withdrawal, SAEs. Additionally, side-effects related to baseline opioid usage, which were present at study entry, will be tracked weekly to detect potential improvement during opioid reduction and thus evaluate Endpoint 5.

Device-related will be defined as a relatedness grade of 3, 4, or 5.

17.2.3. Criterion for Success

No Grade 3 or higher device-related adverse events and fewer than 20% of subjects with Grade 2 device-related adverse events.

17.3. NPNS Tolerability

NPNS tolerability will be quantified based on the percentage of participants who voluntarily withdraw from the study prior to the Extension Phase citing lack of tolerability of NPNS treatment as the primary reason for withdrawal, as quantified by selection of response #3 on a questionnaire similar to the one below.

Primary reason for withdrawal:

- I want to return to my original opioid dosage because:
 - (1) my RLS symptoms have gone up after I reduced my opioid dosage
 - (2) I experienced other opioid withdrawal symptoms after I reduced my opioid dosage
- (3) Use of the NPNS devices was uncomfortable or otherwise intolerable
- (4) Other

CONFIDENTIAL

All information contained in this document is confidential and is the sole property of Noctrix Health, Inc.
 Any reproduction in part or whole without the written permission of Noctrix Health, Inc. is prohibited.

 NOCTRUX HEALTH	Clinical Trial Investigational Plan, Protocol CT-03 (Opioid Reduction Study)	Document #: CT-2 (Previously CT-03) Rev: 4.0 (Superseded Rev C) CC#: 720 (Previously DCO #138) Effective: 09/24/2021
---	---	---

The criterion for success will be fewer than 20% of subjects who begin NPNS treatment withdrawing for this reason.

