16.12. Subject Discontinuation

A subject may be removed from the study prior to completion for any of the following reasons:

- Voluntary withdrawal of consent
- Adverse event preventing further study participation
- Investigator believes risk of further subject participation outweighs benefit
- Persistent non-compliance or lost to follow-up
- Pregnancy
- Subject no longer meets inclusion criteria
- Reduced opioid dosage is not tolerable, as evaluated by the subject or the investigator
- Subject fails to comply with reduced opioid dosage
- Subject changes dosage of non-opioid medications known to interfere with sleep or RLS symptoms, including sleep medications, antidepressants, sedative antihistamines.

The Investigator or research staff will complete a study exit form in the CRF for any subject who prematurely discontinues from the study. If discontinuation was the result of an AE, the AE will also be recorded in the CRF.

Upon discontinuation, subjects will receive partial compensation commensurate with their completed Phases.

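### NPNS tolerability counts only voluntary withdrawals, so a subject the investigator removes for a device reaction scores as a non-failure and the under-20% criterion understates device intolerance

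*Combined protocol and SAP*

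**What the plan says.** Section 17.3 bases tolerability on the "percentage of participants who voluntarily withdraw from the study prior to the Extension Phase citing lack of tolerability of NPNS treatment". This limits the numerator in two ways. The subject must leave voluntarily before the Extension Phase, and the reason is taken from the subject's own answer, "as quantified by selection of response #3 on a questionnaire similar to the one below". The pass rule is: "The criterion for success will be fewer than 20% of subjects who begin NPNS treatment withdrawing for this reason". The denominator is therefore everyone who starts the device.

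Section 16.12 gives a longer list of reasons for leaving. Beside voluntary withdrawal of consent it has "Adverse event preventing further study participation" and "Investigator believes risk of further subject participation outweighs benefit". Neither appears in 17.3.

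The synopsis and Safety Endpoints 3, 5 and 6 in Section 17.2.1 omit the word voluntary, but still need the subject to withdraw and cite the device. Safety Endpoints 4, 7 and 8, on non-RLS opioid withdrawal symptoms, instead count subjects who are discontinued, whoever makes the decision.

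The other limit on device reactions is the safety criterion in Section 17.2.3: "No Grade 3 or higher device-related adverse events and fewer than 20% of subjects with Grade 2 device-related adverse events". Section 17.2.2 adds: "Device-related will be defined as a relatedness grade of 3, 4, or 5". Safety Endpoint 1 in Section 17.2.1 uses a narrower set, Probable or Definite, which is grades 4 and 5 of Table 2.

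**The concern.** An investigator who stops a subject because of a device reaction has recorded intolerance at least as clearly as a subject who ticks a box. Under 17.3 that exit has the same effect on the result as a subject who completed Phase 2 comfortably: it adds one to the denominator and nothing to the numerator.

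The measure then depends partly on who speaks first. Two subjects with the same skin or sensation reaction are scored differently if one asks to stop and the other is stopped. The plan avoids this for opioid-related exits and gives no reason for treating device-related exits otherwise. With 20 to 40 open-label subjects, one or two exits classified the other way can change whether a pre-set pass/fail criterion is met.

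**Working it through.** The plan derives no figure here. The 20% threshold is a stated rule, so the check is a count.

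**Inputs.** Primary-study size N = 20 to 40 (synopsis). Tolerability passes if fewer than 20% of subjects who begin treatment withdraw for the device (17.3). Safety passes if there is no Grade 3 or higher device-related event and fewer than 20% of subjects have a Grade 2 one (17.2.3). I take the same N for both, since 17.2.3 does not define its denominator.

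**Step 1: largest count that passes.** The largest whole k with k/N < 0.20 is:
- N = 20: k = 3 (3/20 = 15%; 4/20 = 20% fails)
- N = 30: k = 5 (5/30 = 16.7%)
- N = 40: k = 7 (7/40 = 17.5%; 8/40 = 20% fails)

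**Step 2: how little it takes.** With N = 20, three response #3 withdrawals and one removal for a device reaction, 17.3 reports 3/20 = 15% and passes. Counting all device exits gives 4/20 = 20% and fails. At N = 40, seven and one give 17.5% against 8/40 = 20%.

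**Step 3: worst case across the two criteria.** Assume that:
- the voluntary withdrawers and the removed subjects are different people;
- both counts sit at their cap;
- no voluntary withdrawer or continuing subject has a Grade 2 device-related event;
- every removal is for a Grade 2 event.

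Total device exits are then 2k, of which k are missed by 17.3.

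| N | Counted by 17.3 | Missed by 17.3 | All device exits |
|---|---|---|---|
| 20 | 3 (15%) | 3 (15%) | 6 (30%) |
| 30 | 5 (16.7%) | 5 (16.7%) | 10 (33.3%) |
| 40 | 7 (17.5%) | 7 (17.5%) | 14 (35%) |

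Over every N from 20 to 40 the total runs from 30.0% (N = 20) to 38.9% (14/36). If every device exit counted towards 17.3, the most that could pass would be k alone.

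**Step 4: illustration with an assumed loss rate.** The documents give no rate of device loss. Assume a true rate t, half voluntary and half removed for Grade 2 events, with no other Grade 2 or higher device-related event. The chance that 17.3 passes now is P(Bin(N, t/2) ≤ k). The chance that 17.3 and 17.2.3 both pass now is the matching trinomial sum. With all device exits counted, the chance is P(Bin(N, t) ≤ k). Each cell gives t = 30%, 1/3 and 35%.

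| N | 17.3 now | 17.3 and 17.2.3 now | 17.3, all device exits |
|---|---|---|---|
| 20 | 0.65, 0.57, 0.53 | 0.39, 0.29, 0.24 | 0.11, 0.06, 0.04 |
| 30 | 0.71, 0.62, 0.57 | 0.48, 0.35, 0.29 | 0.08, 0.035, 0.02 |
| 40 | 0.76, 0.65, 0.60 | 0.55, 0.40, 0.33 | 0.055, 0.02, 0.01 |

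**The case against.** The strongest answer is that removed subjects are not lost to the analysis. One Grade 3 or higher device-related event fails the safety criterion outright. Grade 2 events are capped, under a definition of device-related that reaches down to Possible. Section 16.12 requires an exit form for every premature discontinuation and a CRF record of any adverse event that caused it. On the formula in 17.1.3, a subject removed before completing the Assessment period stays in N and cannot enter X, so the removal also lowers the efficacy result (the last rule on exit measures in 13.2 can be read otherwise). Keeping subject-reported tolerability apart from investigator-graded safety is also a coherent design.

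Most of this stands, and it limits the size of the point. It does not close the gap. The safety criterion counts subjects with an event whether or not they leave, so it does not measure tolerability. Removal for a Grade 1 event is capped by neither rule, although Table 1 describes Grade 1 as needing no intervention, so such removals should be few.

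A reader might infer something stronger: that the study as a whole can pass with about a third of subjects lost to the device. The documents do not support that. They contain no overall pass rule, only separate criteria for efficacy, safety, tolerability and compliance. Half of the 30% or 35% consists of withdrawals that 17.3 already counts. The total needs every assumption in Step 3 at once, and any overlap, or any Grade 2 device-related event in a continuing subject, lowers it. It is not a strict ceiling either, because Grade 1 removals are uncapped. At an assumed one-third loss the two criteria together already fail more often than they pass (joint pass 0.29 to 0.40).

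**Conclusion.** The point holds in a limited form. Section 17.3 scores investigator removals for device reactions as non-failures, so its percentage can only understate device intolerance, never overstate it on this account. The part attributable to the omission is at most 3/20 (15%) or 7/40 (17.5%) of subjects if all such removals are for Grade 2 events and the safety criterion is met. The 30% and 35% totals are a worst case that could pass both criteria, not an expected result. The pass probabilities in Step 4 rest on an assumed loss rate and an assumed even split.

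The study is exploratory and this is not its primary endpoint, so the change is one that should be made rather than one on which the study's conclusions depend.

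**What to change.** In 17.3 and in Safety Endpoints 3, 5 and 6, define the numerator as every exit before the Extension Phase (or, for Endpoints 5 and 6, in the stated phase) whose primary cause is the device: either response #3, or removal by the investigator for a device-related adverse event. Count each subject once. Report the voluntary-only percentage beside it, and bring the tolerability line in the synopsis into step.

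State one definition of device-related for this count. Safety Endpoint 1 in 17.2.1 (Probable or Definite) and 17.2.2 (grades 3, 4 or 5) must be reconciled first, because events graded Possible would be in or out depending on which is used.

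The cost is a short text change. The exit form, the adverse event record and the relatedness grade are already collected, and no clinical rule changes. The reported intolerance rate may be somewhat higher, up to the worst case above, and some subjects will count under both safety and tolerability. The report should say so.
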